8.2.6. Echocardiogram with Doppler

Echocardiography will be performed by a qualified sonographer/physician (and overread by a cardiologist), using a standard, commercially available ultrasound machine. The echocardiography technician should perform standard 2-dimensional (2-D) transthoracic echocardiography with Doppler, as described by the American Society of Echocardiography (ASE) recommendations ([Picard et al., 2011](#)). The full ASE protocol need not be followed but

should include a gross assessment of the overall cardiac anatomy and quantitative evaluation of basic ventricular systolic function. The final echocardiogram report should note the details of the protocol that were followed. The overreading cardiologist should note any findings in the department's standard reporting format. Findings from the echocardiogram should be included in the participant's source record and documented in the eCRF. Any findings that, in the opinion of the Investigator, may disqualify the participant should be discussed with the Medical Monitor.

Additionally, all echocardiogram data will be transmitted to a standalone imaging vendor, where qualified personnel will perform postprocessing of echocardiogram data and central overread of all images. Site personnel will be trained in the processes relating to echocardiogram performance and data transmission.

The end-to-end process of centralized echocardiogram overread and postprocessing is detailed in a separate DCR-PHXC-201 Centralized Imaging Overread plan.

8.2.7. Reporting Fluid Intake

Hyperhydration regimens are a central feature in the conservative management of urinary oxalate levels in patients with PH. As such, participants are asked to maintain a consistent fluid intake throughout the study (Section 5.3). Participants will be asked to report their average daily fluid intake during the 4- to 7-day period before each of the 24-hour urine collections, including the 2 collections conducted during screening.

8.3. ADVERSE EVENTS, SERIOUS ADVERSE EVENTS AND ADVERSE EVENTS OF SPECIAL INTEREST

The definitions of AEs, SAEs, and adverse events of special interest (AESI) are located in Section 10.3.

Adverse events will be reported by the participant (or, when appropriate, by a caregiver, surrogate, or the participant's legally authorized representative).

The Investigator and any qualified designees are responsible for detecting, documenting, and recording events that meet the definition of an AE or SAE and remain responsible for following up AEs that are serious, considered related to the study intervention or study procedures, or that caused the participant to discontinue the study intervention (see Section 7.1).

8.3.1. Time Period and Frequency for Event Assessment

All SAEs will be collected from the signing of the ICF until 30 days after the last day of study participation.

All AEs will be collected from the signing of the ICF until the EOS at the time points specified in the SoA (Section 1.3).

Any medical condition that is present at the time that the participant is screened will be considered as baseline and not reported as an AE. However, if the study participant's condition deteriorates at any time during the study, it will be recorded as an AE.

Investigators are not obligated to actively seek AE or SAE after conclusion of the study participation. However, if the Investigator learns of any SAE, including a death, at any time after a participant has been discharged from the study, and he/she considers the event to be reasonably

related to the study intervention or study participation, the Investigator must notify the Sponsor promptly.

8.3.2. Method of Detecting AEs and SAEs

The method of recording, evaluating, and assessing causality of AE and SAE and the procedures for completing and transmitting SAE reports are provided in Section **10.3.4**.

Adverse events may be reported by the participant (or, when appropriate, by a caregiver, surrogate, or the participant's legally authorized representative) as either unsolicited reports or in response to general questioning, such as "Have you noticed anything different since you began the study?" Care will be taken not to introduce bias when detecting AEs and/or SAEs. Open-ended and non-leading verbal questioning of the participant is the preferred method to inquire about AE occurrences. Participants will be questioned as to the occurrence of muscle pain or weakness. The occurrence of an AE or SAE may also be detected upon review by a study monitor.

8.3.3. Follow up of AEs and SAEs

After the initial AE/SAE report, the Investigator is required to proactively follow each participant at subsequent visits/contacts. All SAEs and non-serious AESI (as defined in Section **10.3.3**), will be followed until resolution, stabilization, the event is otherwise explained, or the participant is lost to follow-up (as defined in Section **7.3**). Further information on follow-up procedures is given in Section **10.3.4**.

8.3.4. Serious Adverse Event Reporting

All SAEs will be recorded and reported to the sponsor or designee immediately; under no circumstance should this exceed 24 hours, as indicated in Section **10.3.5**. The Investigator will submit any updated SAE data to the Sponsor within 24 hours of it being available.

Prompt notification by the Investigator to the Sponsor of a SAE is essential so that obligations and ethical responsibilities towards the safety of participants and the safety of the study intervention under clinical investigation are met.

The Sponsor has a responsibility to notify both the local regulatory authority and other regulatory agencies about the safety of a study intervention under clinical investigation. The Sponsor will comply with country-specific regulatory requirements relating to safety reporting to the regulatory authority, Institutional Review Boards (IRB)/Independent Ethics Committees (IEC), and Investigators.

Investigator safety reports will be prepared for suspected unexpected serious adverse reactions (SUSAR) according to local regulatory requirements and Sponsor policy and will be forwarded to Investigators as necessary.

8.3.5. Reporting of Pregnancy

Details will be collected of all pregnancies in female participants occurring after the start of study intervention and until 12 weeks after the last dose of study intervention.

If a pregnancy is reported, the Investigator should inform the Sponsor within 24 hours of learning of the pregnancy and should follow the procedures outlined in Section **10.4**.

Abnormal pregnancy outcomes (e.g., spontaneous abortion, fetal death, stillbirth, congenital anomalies, and ectopic pregnancy) are considered SAEs.

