4. STUDY DESIGN

4.1. OVERALL DESIGN

This is Phase 2 multicenter trial of DCR-PHXC in patients with primary hyperoxaluria (PH1 and PH2). The primary hypothesis to be tested is that DCR-PHXC is superior to placebo in lowering Uox burden over a 6-month test period.

This is a randomized, placebo-controlled, double-blind, parallel-group trial, in which participants will be randomized in a 2 to 1 ratio (DCR-PHXC to placebo). An adaptive randomization via minimization method will be used to allocate patients to treatment groups with respect to age and eGFR. See Section 9.3 for details of the minimization scheme.

Following the up-to-35-day screening period, participants will return to the clinic for interim visits through Day 180. Note: an extra 7 days will be allowed for participants who are required to repeat screening 24-hour urine collections or for repeat of initially unanalyzable screening laboratory assessment samples. The total time on study for each participant is approximately 7 months. Participants completing this study may be eligible for enrollment into a long-term open-label extension study (see Section 6.7).

It is expected that the entire trial will have an 18-month duration.

Blinding will be maintained using an unblinded pharmacist or designee and tinting or shrouding of the administration syringe to obscure the slight color difference between DCR-PHXC and placebo.

It is expected that approximately 40 participants will be screened, such that 36 participants will be evaluable.

An interim analysis of the data may be conducted when two-thirds of participants have completed study assessments through the Day 180 visit. See Section 9.6 for details of the interim analysis.

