4.4. END OF STUDY DEFINITION

A participant is considered to have completed the study if he or she has completed all phases of the study including the last visit or the last scheduled procedure shown in the Schedule of Activities (SoA), Section 1.3.

The end of the study is defined as completion of the last visit or procedure shown in the SoA in the trial globally.

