10.4.2. Contraception Guidance

Male participants

Male participants with female partners of childbearing potential are eligible to participate if they agree to ONE of the following from Day 1 through 12 weeks after the last dose of study intervention:

- Are abstinent from penile-vaginal intercourse as their usual and preferred lifestyle (abstinent on a long-term and persistent basis) and agree to remain abstinent
- Agree to use a male condom plus partner use of a contraceptive method with a failure rate of < 1% per year, as described in **Table 5**, when having penile-vaginal intercourse with a WOCBP who is not currently pregnant

Male participants must refrain from donating sperm for the duration of the study and for 12 weeks after the last dose of study intervention.

Male participants with a pregnant or breastfeeding partner must agree to remain abstinent from penile-vaginal intercourse or use a male condom during each episode of penile penetration during the protocol-defined time frame.

Female participants

Female participants of childbearing potential are eligible to participate if they agree to use a highly effective method of contraception consistently and correctly throughout the study and for 12 weeks following the last dose of study intervention, as described in Table 5.

Table 5: Highly Effective Contraceptive Methods

Highly Effective Contraceptive Methods That Are User Dependent^a Failure rate of <1% per year when used consistently and correctly.

 • Combined (estrogen- and progestogen-containing) hormonal contraception associated with inhibition of ovulation 
 • Oral • Intravaginal • Transdermal

 • Progestogen-only hormonal contraception associated with inhibition of ovulation 
 • Oral • Injectable

Highly Effective Methods That Are User Independent^a

 • Implantable progestogen-only hormonal contraception associated with inhibition of ovulation 
 • Intrauterine device (IUD) • Intrauterine hormone-releasing system (IUS) • Bilateral tubal occlusion

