10.4.4. Collection of Pregnancy Information

Male participants with partners who become pregnant

- The Investigator will attempt to collect pregnancy information on any male participant's female partner who becomes pregnant while the male participant is in this study.
- After obtaining the necessary signed informed consent from the pregnant female partner directly, the Investigator will record pregnancy information on the appropriate form and submit it to the Sponsor within 24 hours of learning of the partner's pregnancy. The female partner will also be followed to determine the outcome of the pregnancy. Information on the status of the mother and child will be forwarded to the Sponsor. Generally, the follow-up will be no longer than 6 to 8 weeks following the estimated delivery date. Any termination of the pregnancy will be reported regardless of fetal status (presence or absence of anomalies) or indication for the procedure.

Female Participants who become pregnant

- The Investigator will collect pregnancy information on any female participant who becomes pregnant while participating in this study. Information will be recorded on the appropriate form and submitted to the Sponsor within 24 hours of learning of a participant's pregnancy.
- The participant will be followed to determine the outcome of the pregnancy. The Investigator will collect follow-up information on the participant and the neonate and the information will be forwarded to the Sponsor. Generally, follow-up will not be required for longer than 6 to 8 weeks beyond the estimated delivery date. Any termination of pregnancy will be reported, regardless of fetal status (presence or absence of anomalies) or indication for the procedure.
- While pregnancy itself is not considered to be an AE or SAE, any pregnancy complication or elective termination of a pregnancy will be reported as an AE or SAE. A spontaneous abortion is always considered to be an SAE and will be reported as such. Any post-study pregnancy related SAE considered reasonably related to the study intervention by the Investigator will be reported to the Sponsor as described in Section 10.3.5. While the Investigator is not obligated to actively seek this information in former study participants, he or she may learn of an SAE through spontaneous reporting.
- Any female participant who becomes pregnant while participating in the study will discontinue study intervention.

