- a) Because participants entering the Study are naïve to DCR-PHXC, administration of blinded study intervention at the first 3 visits (Days 1, 30, and 60) must occur at the clinical site, along with all protocol-specified safety assessments.

- b) Should the site encounter difficulty with the duration or frequency of blood sampling for PK at Days 1 or 30:
 - i) the schedule in adults may be abbreviated to include only the predose and 4-hour samples; with the samples scheduled at 5, 15, and 30 minutes and 1, 2, 6, 10, and 12 hours postdose being omitted;
 - ii) the schedule in children aged 6 to 17 may be abbreviated to include only predose and 4 hours postdose; with the samples scheduled at 30 minutes and at 2 and 10 hours postdose being omitted.

3) Study Visits for Days 2 and 31

- a) At-clinic site visits are not required for Visits at Days 2 and 31. A combination of telemedicine and home nursing care will allow participants to undergo “virtual” visits.
- b) The Investigator (or designee) is expected to call the participant on these visit days to assess the participant’s overall health status and to record any AE or SAEs.
- c) The 24-hour postdose blood sample for PK analysis should be collected as scheduled (participants \geq 18 years of age).

4) Study Visits for Days 15, 45, 90, 120, and 150

- a) At-clinic site visits are not required for Visits at Day 15, 45, 90, 120, and 150. A combination of telemedicine and home nursing care will allow participants to undergo “virtual” visits.
- b) Dicerna is working with the Illingworth Nursing Group to extend their responsibilities for collection and processing of safety labs and vital signs, as well as for administration of double-blind study intervention.
- c) On Days 90, 120, and 150, the home nurse will call the Investigator the day before the scheduled home visit to obtain permission to administer study intervention to the participant. The nurse will follow-up with the Investigator again on the day after the home visit.
- d) The Investigator (or designee) is expected to call the participant on these visit days to assess the participant’s overall health status and to record any AE or SAEs.
- e) The specific responsibilities of the home nurses and the execution of the virtual visits will be outlined in an at-home nursing visit guidance.

5) Study Visits for Day 180

- a) The Day 180 Visit (with End-of-Study assessments) must occur at the clinical site due to the required imaging procedures.

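### Partner pregnancies are collected only while the man is in the study, although the protocol's own precautions for men run to 12 weeks after the last dose

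*Protocol*

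**What the plan says.** Three parts of the protocol bear on this.

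- **8.3.5 (reporting).** Details are collected of "all pregnancies in female participants occurring after the start of study intervention and until 12 weeks after the last dose" of study intervention. Partners of male participants are not mentioned. For procedures, the section refers to 10.4.
- **10.4.4 (collection).** For women, it covers "any female participant who becomes pregnant while participating in this study". For partners, it covers "any male participant's female partner who becomes pregnant while the male participant is in this study". Neither sentence gives a period after the last dose.
- **10.4.2 (contraception).** Men with partners of childbearing potential must follow the stated precautions "from Day 1 through 12 weeks after the last dose of study intervention". The ban on sperm donation ends at the same point. Inclusion criterion 6 in 5.1 repeats the 12 weeks.

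On timing, the Schedule of Activities (1.3) places the last dose at Day 150 and the end-of-study visit at Day 180, each with a window of 5 days either way. Section 4.1 says that "participants will return to the clinic for interim visits through Day 180". Under 4.4, a participant has completed the study once he or she has "completed all phases of the study including the last visit or the last scheduled procedure shown in the Schedule of Activities".

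Section 6.7 adds monthly follow-up for participants who do not enter the extension study DCR-PHXC-301. It lasts until Uox is back to at least 80% of baseline. Sections 7.1 and 7.2 set the same rule for those who stop treatment or withdraw.

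**The concern.** The protocol asks men to take precautions for 12 weeks after the last dose, so it treats a conception in that period as relevant. The only rule for collecting partner pregnancies stops when the man leaves the study. For a completer that is about 30 days after the last dose. A site that follows the text would have no instruction to record a partner pregnancy arising later in the precaution period, or to seek the partner's consent and follow the outcome.

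What is at stake is completeness of pregnancy reporting. No endpoint, analysis population or test is affected. Few such pregnancies are likely in a trial of about 36 participants, but one that is not reported is hard to recover later.

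**Working it through.** The protocol states no figure for this gap, so there is none to reproduce. The check is calendar arithmetic.

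**Inputs**

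- Precaution period for men (10.4.2): 12 × 7 = 84 days after the last dose.
- Last scheduled dose (1.3): Day 150, window 145 to 155.
- Last visit (1.3, 4.1): Day 180, window 175 to 185.
- Partner collection (10.4.4): ends when the man is no longer in the study. By 4.4, for a completer, that is the last visit.

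**Formula**

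Days covered = day of last visit − day of last dose.
Gap = 84 − days covered, or 0 if that is negative.

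| Last dose | Last visit | Covered | Gap | Share of 84 days |
|---|---|---|---|---|
| Day 150 | Day 180 | 30 | 54 | 54/84 = 64.3% |
| Day 145 | Day 185 | 40 | 44 | 44/84 = 52.4% |
| Day 155 | Day 175 | 20 | 64 | 64/84 = 76.2% |
| Day 120 | Day 180 | 60 | 24 | 24/84 = 28.6% |
| Day 90 | Day 180 | 90 | 0 | 0% |

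In the nominal case the period ends on Day 150 + 84 = Day 234, and 234 − 180 = 54.

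**If the Uox follow-up counts as being in the study**

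The gap then becomes 234 minus the day on which follow-up ends. The documents do not say how long it lasts. Assuming 30-day months, follow-up that ends after one month (Day 210) leaves 234 − 210 = 24 days, and follow-up that ends after two months (Day 240) leaves none.

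Who would be in follow-up can be gauged from the plan's own figures. Section 9.2 assumes a 40% fall on active treatment, which is 60% of baseline and below the 80% threshold. It assumes no net change on placebo, so a typical placebo participant would meet the threshold at once.

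**The serious adverse event (SAE) tail**

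Section 8.3.1 collects SAEs until 30 days after the last day of participation, which is Day 180 + 30 = Day 210. Even if it applied to partners, 234 − 210 = 24 days would remain.

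**Women**

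Section 8.3.5 runs to 12 weeks after the last dose and 10.4.4 runs to the end of participation. The two differ, but the longer window is stated outright in the section headed as the reporting rule.

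**The case against.** The strongest reply is the follow-up in 6.7, 7.1 and 7.2. A man on active treatment who does not roll over will probably still be below 80% of baseline at Day 180, so he stays in monthly contact. Those sections ask for fresh consent only after six months, which suggests that the earlier follow-up runs under the study consent. On that reading the 54 days fall mainly on placebo participants, who had no drug exposure, and on men on active treatment whose Uox fell little.

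Much of this stands. It is why a reader should not infer that most of the post-dose period is uncovered for partners in general. It does not remove the point. The follow-up ends on a Uox value and not at 12 weeks, its pregnancy testing concerns participants, and partners are not mentioned. Section 6.7 is headed as dealing with the time after the study, and nothing says that this follow-up counts as being in the study.

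A second reply is that there are backstops. Section 8.3.1 asks for prompt notice of a related SAE learned of after discharge, and 8.3.5 classes abnormal pregnancy outcomes as SAEs. Section 10.4.4 has a similar clause on post-study events. These are passive, limited to SAEs judged related, and do not clearly reach partners; the 10.4.4 clause sits under female participants. They soften the gap without closing it.

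A reader might also infer that women are left uncovered after Day 180. The documents do not support that. Section 8.3.5 gives women the full 12 weeks and sends sites to 10.4 for procedures. The narrower phrase in 10.4.4 is a conflict of wording.

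Finally, participants who enter DCR-PHXC-301 come under rules that are not in these documents, so nothing can be said about them here.

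**Conclusion.** The point holds for partners of male participants, under conditions. No section carries partner-pregnancy collection to the end of the period that 10.4.2 sets for men. The gap is 54 of 84 days (64%), or 44 to 64 days (52% to 76%) across the visit windows, for a man who:

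- took the Day 150 dose and completed at Day 180;
- did not roll over; and
- is not in the Uox follow-up, or is in it but not counted as in the study.

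The gap is smaller if that follow-up counts. It is 24 days after a last dose on Day 120, and nil after a last dose on Day 90 or earlier with a stay to Day 180. For women, the two sections need reconciling, but no gap in collection is shown.

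The severity is minor: this is a safety-reporting inconsistency in a small trial, with no effect on the efficacy analysis. The conclusion takes the 12 weeks as the protocol states them and expresses no view on whether that length is right.

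**What to change.** Reconcile 8.3.5 and 10.4.4 to one stated collection window that names both female participants and partners of male participants and matches the period already set in 10.4.2. At the last visit, ask participants to report any pregnancy that arises within it. For a man last dosed on Day 150, collection would then run to Day 234 and leave none of the 84 days uncovered, whether or not the Uox follow-up counts as study participation.

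The cost is a wording change in two sections plus the reminder; no new visit or test is needed. The downside is a few more reports. Each partner case needs her own signed consent and follow-up of the outcome, generally to no later than 6 to 8 weeks past the estimated delivery date, as 10.4.4 already requires.

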8.4. TREATMENT OF OVERDOSE

For this study, any dose of study intervention greater than the protocol-specified dose will be considered an overdose.

In the event of an overdose, the Investigator should:

1. Contact the Medical Monitor immediately.
2. Closely monitor the participant for any AE/SAE and laboratory abnormalities until study intervention can no longer be detected systemically (at least 28 days).
3. Obtain a plasma sample for PK analysis if requested by the Medical Monitor (determined on a case-by-case basis).
4. Document the quantity of the excess dose as well as the duration of the overdose in the CRF.

Decisions regarding dose interruptions will be made by the Investigator in consultation with the Medical Monitor based on the clinical evaluation of the participant.

